### 9.3.1. Solicited Events and Symptoms

Systemic solicited AEs were collected pre-vaccination, and systemic and local solicited AEs were collected 30 minutes post-vaccination and then daily for 7 days after each vaccination. Solicited local events include erythema (redness), induration (hardness)/edema (swelling), pain, and tenderness. Solicited systemic events include fever, chills (feverishness), fatigue (tiredness), malaise (general unwell feeling), myalgia (body aches/muscular pain exclusive of the injection site), arthralgia (joint pain exclusive for the injection site), headache, nausea, and diarrhea. Solicited events were graded on a scale of none (absent), mild, moderate, and severe. Measurement values for erythema and induration (hardness)/edema (swelling) were collected and graded based on the FDA Toxicity Grading Scale for Healthy Adult and Adolescent Volunteers Enrolled in Preventative Vaccine Clinical Trials [[4](#)].

Solicited AEs are summarized by severity pre-vaccination (systemic solicited AEs only), post-vaccination, and each day post-study vaccination (Days 1-8). Solicited AEs are also summarized by the maximum severity over all post-vaccination measurements. The proportions of participants reporting each symptom, any local symptom, any systemic symptom, and any symptom are summarized by vaccination arm separately for each dose and both doses combined (where applicable). For each event the denominator is the number of participants with non-missing data for the event.

The following summaries for solicited adverse events are presented by maximum severity, vaccination (each dose separately and both doses combined, where applicable), and vaccination arm:

- Number and percentage of participants experiencing solicited events by symptom and maximum severity, for any symptom, local symptoms, and systemic symptoms (beginning with [Table 222](#) and ending with [Table 230](#))
- Number and percentage of participants experiencing any solicited event, any systemic event, any local symptom, and each symptom, by day and severity, for each vaccination (starting with [Table 231](#) and ending with [Table 250](#))

- Duration of solicited symptoms summarized by mean, standard deviation, median, minimum, and maximum by symptom, dose, and vaccination arm ([Table 251](#), [Table 252](#), [Table 253](#), [Table 254](#), and [Table 255](#))
- Bar graphs of the number of participants experiencing a symptom by severity and day for systemic symptoms (beginning with [Figure 543](#) and ending with [Figure 551](#)) and for local symptoms (beginning with [Figure 552](#) and ending with [Figure 560](#))
- Bar graphs of the number of participants experiencing the onset of a symptom by the severity and day for systemic symptoms (beginning with [Figure 561](#) and ending with [Figure 569](#)) and local symptoms (beginning with [Figure 570](#) and ending with [Figure 578](#))
- Figures of solicited symptoms by day, dose, and vaccination arm for each participant, separated by symptom (beginning with [Figure 579](#) and ending with [Figure 653](#))

### 9.3.2. Unsolicited Adverse Events

The proportion of participants reporting at least one unsolicited adverse event are summarized by MedDRA system organ class and preferred term for each dose and both doses combined, where applicable. Denominators for percentages are the number of participants who received the vaccination.

The following summaries for unsolicited adverse events will be presented by vaccination arm:

- Frequency of AEs by MedDRA system organ class (SOC), severity, and relationship to study vaccination (beginning with [Table 256](#) and ending with [Table 272](#))
- Frequency of AEs by MedDRA SOC, MedDRA preferred term, severity, and relationship to study vaccination (beginning with [Table 273](#) and ending with [Table 289](#))
- Participant incidence of AEs (number and percentage of participants experiencing AEs) by MedDRA SOC, MedDRA preferred term, severity, and relationship to study vaccination (beginning with [Table 290](#) and ending with [Table 306](#))
- Frequency of AEs (number and percentage of participants experiencing AEs) by MedDRA SOC and severity ([Figure 654](#), [Figure 655](#), [Figure 656](#), [Figure 657](#), and [Figure 658](#))
- Participant incidence of AEs (number and percentage of participants experiencing AEs) by MedDRA SOC and severity ([Figure 659](#), [Figure 660](#), [Figure 661](#), [Figure 662](#), and [Figure 663](#))
- Participant listing of all unsolicited adverse events ([Listing 11](#))
- Participant listing of serious adverse events ([Table 307](#))
- Participant listing of non-serious adverse events of moderate or greater severity ([Table 308](#))
- Participant listing of other significant adverse events, which includes AESIs, PIMMCs, MAAEs, and NOCMCs ([Table 309](#))

### 9.4. Deaths, Serious Adverse Events and other Significant Adverse Events

Individual participant listings of serious adverse events and adverse events of special interest, which includes medically attended adverse events, potentially immune-mediated medical conditions, and new onset chronic medical conditions will be presented ([Table 307](#), [Table 309](#)).

## 9.5. Pregnancies

Urine or serum pregnancy tests will be performed at the screening visit and within 24 hours prior to each study vaccination. Results must be negative to ensure eligibility and continuation of study treatment. For pregnancies occurring in study participants, a venous blood sample for serological assays will be collected per protocol with participant permission. Large volume blood samples for cellular immunological assays will be discontinued. The participant will be followed for the duration of the study. Efforts will be made to follow all pregnancies reported during the study to pregnancy outcome with participant permission.

The following individual participant listings will be presented for pregnancies and outcomes (Appendix 16.2.11):

- Maternal information ([Listing 17](#))
- Gravida and para ([Listing 18](#))
- Live birth outcomes ([Listing 19](#))
- Still birth outcomes ([Listing 20](#))
- Spontaneous, elective, or therapeutic abortion outcomes ([Listing 21](#))

## 9.6. Clinical Laboratory Evaluations

Chemistry parameters measured include alanine aminotransferase, aspartate aminotransferase, alkaline phosphatase, total bilirubin, creatine kinase, and creatinine. Hematology parameters measure include white blood cells, hemoglobin, and platelets.

Summaries of clinical laboratory data are grouped by vaccination arm, severity for each visit, and the maximum over all post-vaccination visits. Summaries are shown for each chemistry parameter and all chemistry parameters combined ([Table 312](#), [Table 313](#), [Table 314](#), [Table 315](#), [Table 316](#), [Table 317](#), and [Table 318](#)) and for each hematology parameter and all hematology parameters combined ([Table 325](#), [Table 326](#), [Table 327](#), and [Table 328](#)). Clinical laboratory results and change from baseline are also summarized by mean, standard deviation, median, minimum, and maximum for each chemistry parameter ([Table 319](#), [Table 320](#), [Table 321](#), [Table 322](#), [Table 323](#), and [Table 324](#)) and for each hematology parameter ([Table 329](#), [Table 330](#), and [Table 331](#)). Bar graphs of clinical laboratory results by maximum severity post baseline and vaccination arm will be presented [Figure 664](#), [Figure 665](#), [Figure 666](#), [Figure 667](#), and [Figure 668](#)).

Individual participant listings for abnormal chemistry results ([Table 310](#)) and abnormal hematology results ([Table 311](#)) will be presented.

## 9.7. Vital Signs and Physical Evaluations

Vital signs including oral temperature, pulse, and systolic and diastolic blood pressure will be taken at each in-clinic visit. Vital signs assessed on Day 1 prior to the first study vaccination will be considered as baseline. Vital signs will be graded using the FDA Toxicity Grading Scale for Healthy Adult and Adolescent Volunteers Enrolled in Preventative Vaccine Clinical Trials [4] and recorded by severity as mild/grade 1, moderate/grade 2, severe/grade 3, and potentially life threatening/grade 4. Results will be tabulated by time point, severity, and vaccination arm for each vital sign and all vital signs combined ([Table 332](#), [Table 333](#), [Table 334](#), [Table 335](#), and [Table 336](#)).

Individual participant listings of vital signs will be presented ([Listing 14](#)).

A targeted physical examination may be performed, if indicated, based on review of interim medical history. Height and weight will be collected on Day 1 prior to the first study vaccination to calculate BMI, which will be presented with continuous demographics ([Table 42](#), [Table 43](#), [Table 44](#), [Table 45](#), and [Table 46](#)). Individual participant listings of physical exam findings will be presented ([Listing 15](#)).

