### 3.1. Study Definitions and Derived Variables

Vital signs, including oral temperature, pulse, and blood pressure (BP), and clinical laboratory parameters obtained prior to the first study vaccination will be considered as baseline. Blood drawn for cellular immunology assays, antibody assays, and transcriptomal assays (groups 5-11, 13-15 only) prior to the first dose of study product will be considered as baseline in immunogenicity analyses.

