## 6. GENERAL STATISTICAL CONSIDERATIONS

### 6.1. General Principles

Unless otherwise noted, continuous variables will be summarized using the following descriptive statistics: n (non-missing sample size), mean, standard deviation, median, maximum and minimum. The frequency and percentages (based on the non-missing sample size) of observed levels will be reported for all categorical measures.

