**Table 330: Laboratory Summary Statistics by Parameter, Time Point, and Vaccination Arm – Hemoglobin**

**Table 331: Laboratory Summary Statistics by Parameter, Time Point, and Vaccination Arm – Platelets**

### 14.3.6 Displays of Vital Signs

**Table 332: Vital Signs by Assessment, Maximum Severity, Time Point, and Vaccination Arm – Any Assessment**

Time Point	Vaccination Arm	N	None		Mild		Moderate		Severe		Missing	
			n	%	n	%	n	%	n	%	n	%
Baseline	Group 1: $5 \times 10^{10}$ vp ChAd/ 30 µg SAM-S	x	x	xx	x	xx	x	xx	x	xx	x	xx
	Group 3A: 30 µg SAM-S/ 30 µg SAM-S											
	Group 3B: 30 µg SAM-S/ 3 µg SAM-S											
	Group 4: 10 µg SAM-S-TCE/ 3 µg SAM-S-TCE											
	Group 5: 3 µg SAM-S-TCE											
	Group 6: 6 µg SAM-S-TCE											
	Group 9: 3 µg SAM-S-TCE											
	Group 10: 6 µg SAM-S-TCE											
	Group 11: 10 µg SAM-S-TCE											
	Group 13: $5 \times 10^{10}$ vp ChAd-S-TCE											
	Group 14: $1 \times 10^{11}$ vp ChAd-S-TCE											
	Group 15: $5 \times 10^{11}$ vp ChAd-S-TCE											
	All Participants											
Day 2												
Day 8	...											
Day 15												
Day 29	...											
Day 36	...											
Day 43	...											
Day 57	...											
Day 85												

Time Point	Vaccination Arm	N	None		Mild		Moderate		Severe		Missing	
			n	%	n	%	n	%	n	%	n	%
Day 86												
Day 92												
Day 99												
Day 113												
Day 169												
Day 181												
Day 209												
Day 265												
Day 366												
Day 394	...											
Day 450												
Max Severity Post Baseline	...											

Note: The “Max Post Baseline” rows indicate the maximum severity experienced by each participant at any time point post baseline, including unscheduled assessments.  
N = Number of participants in the safety population.

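### Vital signs are summarised by arm only as toxicity-grade counts; adding value and change-from-baseline tables, as already planned for laboratory results, would show a shift below the grading limits

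*SAP*

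**What the plan says.** Section 9.7 of the SAP has oral temperature, pulse and systolic and diastolic pressure taken at each in-clinic visit and graded on the FDA toxicity scale. It fixes a baseline: "Vital signs assessed on Day 1 prior to the first study vaccination will be considered as baseline". Section 3.1 says the same of vital signs and laboratory parameters "obtained prior to the first study vaccination will be considered as baseline". The planned summary is then: "Results will be tabulated by time point, severity, and vaccination arm for each vital sign and all vital signs combined".

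Table 332 ("Vital Signs by Assessment, Maximum Severity, Time Point, and Vaccination Arm – Any Assessment") has columns for N, None, Mild, Moderate, Severe and Missing, a baseline block, a block for each later visit and a row for maximum severity after baseline. Tables 333-336 use the same format for the individual signs. Section 9.7 also says "Individual participant listings of vital signs will be presented" (Listing 14). Section 9.9 plans no further safety analyses.

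For laboratory results, Section 9.6 plans grade tables and also continuous ones: "Clinical laboratory results and change from baseline are also summarized by mean, standard deviation, median, minimum, and maximum for each chemistry parameter". The same is planned for hematology (Tables 319-324 and 329-331).

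**The concern.** Four continuous measurements with a defined baseline are reduced to four categories in every by-arm table. No vital-sign table calculates a change from that baseline. This includes the Day 2 clinic visit of the Stage 2 groups (Table 8), the day after dosing.

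The grading scale does not force this, because Section 9.6 grades laboratory values on the same scale and still summarises them as numbers. The vital-sign shell also lacks the low/high split of the laboratory shells, so if a sign is graded in both directions, the two share a cell.

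The primary objective is safety and tolerability at different doses. A shift in pulse or blood pressure that moves most of a group without taking many participants past a grading limit would show weakly in these tables, and its size would not be reported at all.

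**Working it through.** **The plan's own figures.** The SAP gives no detectability figure for vital signs. Its only safety figures are the binomial probabilities in Table 4, and all 16 rows reproduce. For example, with n = 10 and a true rate of 20%, the chance of at least one event is 1 − 0.8^10 = 89.3%, as printed.

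**Inputs from the SAP (Table 2).** Groups 1, 3A and 4 have 4, 3 and 3 participants. Group 3B has 7. The Stage 2 groups that enrolled are planned at 7 to 12.

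**Inputs assumed.** None of these is in the SAP:
- a shift of d = 1 SD of within-person change;
- a proportion p0 of 2%, 5%, 10% or 20% at Grade 1 or above without a shift;
- normal values, with equal SD for the value and for the change (a within-person correlation of 0.5).

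**Mean change.** This is the probability that the two-sided 95% t interval excludes zero, from the noncentral t distribution with n − 1 degrees of freedom and noncentrality d√n. For n = 10 the noncentrality is 3.16, the critical value is 2.262 and the probability is 80.3%.

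**Graded proportion.** After the shift, p1 = 1 − Φ(z(1−p0) − d). Find the smallest count whose Clopper-Pearson lower limit exceeds p0, then take the binomial probability of reaching it. For n = 10:

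| p0 | p1 | Count needed | Probability |
|---|---|---|---|
| 2% | 14.6% | 2 | 44.1% |
| 5% | 26.0% | 3 | 50.3% |
| 10% | 38.9% | 4 | 59.0% |
| 20% | 56.3% | 6 | 53.8% |

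The gap at n = 10 is 80.3 − 59.0 = 21 to 80.3 − 44.1 = 36 percentage points.

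**Other group sizes, 1 SD shift:**

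| n | Mean change | Graded proportion |
|---|---|---|
| 3 | 18% | 6-18% |
| 4 | 29% | 10-28% |
| 7 | 60% | 26-34% |
| 10 | 80% | 44-59% |
| 12 | 88% | 53-77% |

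**Sensitivity.** With a 0.75 SD shift and n = 10, the figures are 56% against 25-34%. With a 0.5 SD shift, mean change itself reaches only 29% at n = 10. The 95% half-width for mean change is t/√n in SD units: 4.303/√3 = 2.48 at n = 3 and 2.262/√10 = 0.72 at n = 10.

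**A second model.** Put the Grade 1 limit k SD above the baseline mean and ask how often a group of 10 has at least one graded participant after a 1 SD shift. For k = 3 this is 21%. For k = 2 it is 82%, against 21% with no shift. Grade counts are therefore weak when the limit is far from the group's mean and much less so when it is near.

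**The case against.** The case against making much of this is substantial, and most of it stands.

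- **Section 6.1 is not breached.** It says "continuous variables will be summarized using the following descriptive statistics: n (non-missing sample size), mean, standard deviation, median, maximum and minimum", but the sentence opens with an exception for anything noted otherwise, and Section 9.7 specifies another display. A reader might infer a contradiction; the text does not support one.
- **The raw values are not lost.** Listing 14 gives every scheduled and unscheduled value by arm, participant and visit. With at most 12 per group, changes can be worked out by hand. A listing still gives no summary of change by arm and visit.
- **Temperature has a second route.** Fever is a solicited event, recorded daily for 7 days after each dose and tabulated by severity. That does nothing for pulse or blood pressure.
- **The baseline is displayed.** Table 332 shows baseline grades beside later grades. What is missing is a within-person change.
- **Vital signs are not named as an endpoint source.** Section 4.5 derives the safety endpoints from adverse events and laboratory results, and Section 6.8 rules out hypothesis testing. The addition must therefore be descriptive. Section 9.7 nevertheless plans five vital-sign tables.
- **The probabilities compare one group with zero.** They do not compare doses. For a 1 SD difference in mean change between two groups, a two-sample t comparison gives only 41%, 56% and 65% at 7, 10 and 12 per group. With no control group, a nonzero change may also reflect the visit itself and not the vaccine.

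**Conclusion.** The gap is real but modest. The by-arm summaries of vital signs are grade counts only, while laboratory results on the same scale also get values and changes from baseline. A shift mostly below the grading limits would be poorly summarised, mainly in groups of 7 to 12. Under the assumed 1 SD shift and 2-20% background, the probabilities at n = 10 are 80% for mean change and 44-59% for the graded proportion. These show the direction and rough size of the loss. They are not properties of the plan, because the shift, the background and the equal SDs are assumptions, and the plan sets no interval for graded vital signs.

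A reader might infer that a dose-related shift would go largely undetected in all groups. The documents do not support that. The same calculation gives roughly even detection from grades at n = 10, Listing 14 holds every value, and at n = 3-4 mean change does little better (18-29%). Nothing in the SAP shows that an endpoint or an escalation decision would change. This is an inexpensive improvement to reporting, not an error in the analysis.

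**What to change.** Keep Tables 332-336. Add to Section 9.7 four tables in the Table 319 format, one each for temperature, pulse, systolic pressure and diastolic pressure. Each gives the value and the change from Day 1 pre-dose by time point and vaccination arm, with n, mean, SD, median, minimum and maximum.

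Optionally add a descriptive 95% t interval for mean change at the first clinic visits after each dose (Day 2 or Day 86 where vital signs are taken, and Day 8, 36 or 92). State that the intervals describe change within a group, are not tests between doses, and carry no multiplicity control.

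The data are already collected and the shell exists. The cost is four tables and slightly more output to read.

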## 9.8. Concomitant Medications

Concomitant medications will be coded to the Anatomical Therapeutic Classification using the WHODrug Dictionary. Concomitant medications are defined in Section 9.1.2 of the protocol. The use of prior and concomitant medications taken during the study will be recorded on the appropriate DCF. The use of concomitant medications during the study will be summarized by ATC1, ATC2 code, and vaccination arm ([Table 337](#), [Table 338](#), [Table 339](#), [Table 340](#), and [Table 341](#)). Individual participant listings of the use of concomitant medications during the study will be presented ([Listing 16](#)).

## 9.9. Other Safety Measures

No additional safety analyses are planned.

## **10. PHARMACOKINETICS**

Not applicable.

## 11. IMMUNOGENICITY

See Section 8.

## **12. OTHER ANALYSES**

Not applicable.

### 13. REPORTING CONVENTIONS

The mean, standard deviation, and other statistics will be reported to 1 decimal place greater than the original data. The minimum and maximum will use the same number of decimal places as the original data. Proportions will be presented as 2 decimal places; values greater than zero but <0.01 will be presented as “<0.01”. Percentages will be reported to the nearest whole number; values greater than zero but < 1% will be presented as “<1”; values greater than 99% but less than 100% will be reported as >99%. Estimated parameters, not on the same scale as raw observations (e.g., regression coefficients) will be reported to three significant figures.

## **14. TECHNICAL DETAILS**

SAS version 9.4 or above will be used to generate all tables, figures, and listings.

**15. SUMMARY OF CHANGES IN THE CONDUCT OF THE STUDY OR  
PLANNED ANALYSES**

See the summary of changes for the protocol for changes in the conduct of the study.

## **17. LISTING OF TABLES, FIGURES, AND LISTINGS**

Table, figure, and listing shells are presented in [Appendix 1](#), [Appendix 2](#), and [Appendix 3](#).

## APPENDICES

**APPENDIX 1. TABLE MOCK-UPS***Notes:*

Tables labelled “COVID-19 Vaccination Naïve, 18-60 years of age, Groups 1 and 3A” include Groups 1 and 3A. Column headers for the groups will be Group 1:  $5 \times 10^{10}$  vp ChAd-S/30  $\mu$ g SAM-S and Group 3A: 30  $\mu$ g SAM-S/30  $\mu$ g SAM-S.

Tables labelled “COVID-19 Vaccination Naïve, 18-60 years of age, Groups 3B and 4” include Groups 3B and 4. Column headers for the groups will be Group 3B: 30  $\mu$ g SAM-S/3  $\mu$ g SAM-S and Group 4: 10  $\mu$ g SAM-S-TCE/3  $\mu$ g SAM-S-TCE.

Tables labelled “COVID-19 mRNA Vaccinated, 18-60 years of age, SAM-S-TCE Boosts” include Groups 5 and 6. Column headers for the groups will be Group 5: 3 $\mu$ g SAM-S-TCE, Group 6: 6  $\mu$ g SAM-S-TCE.

Tables labelled “COVID-19 mRNA Vaccinated, >60 years of age, SAM-S-TCE Boosts” include Groups 9, 10, and 11. Column headers for the groups will be Group 9: 3  $\mu$ g SAM-S-TCE, Group 10: 6  $\mu$ g SAM-S-TCE, Group 11: 10  $\mu$ g SAM-S-TCE. Group 10 is Groups 10A and 10B combined. Group 11 is Groups 11A and 11B combined.

Tables labelled “COVID-19 mRNA Vaccinated, >60 years of age, ChAd-S-TCE Boosts” include Groups 13, 14, 15. Column headers for the groups will be Group 13:  $5 \times 10^{10}$  vp ChAd-S-TCE, Group 14:  $1 \times 10^{11}$  vp ChAd-S-TCE, Group 15:  $5 \times 10^{11}$  vp ChAd-S-TCE.

## 9.1 Overall Study Design and Plan Description

See [Table 2](#).

**9.5.1 Efficacy/Immunogenicity and Safety Measurements Assessed and Flow Chart****Table 6: Schedule of Activities - COVID-19 Vaccination Naïve, 18-60 years of age, Groups 1 and 3A**

Study Visit	V00	V01	V02	V03	V04	V05	V06	V07	V08	V08A	V09	V10	V11	Unsc	Early Term
Study Day post 1 st Study Vaccination	Scr-30d to -1d	D1	D2+1d	D4+2d	D8 +2d	D29±3d	D30+1d	D32+2d	D36+2d	D43+4wk	D57±3d	D209±14d	D394±14d		
Study Day post 2 nd Study Vaccination						D1	D2+1d	D4+2d	D8+2d	D15+4wk	D29±3d	D181±14d	D366±14d		
Obtain Written Informed Consent	X									X					
Review Eligibility Criteria	X	X				X				X					
Medical History	X														
Review Interim Medical History		X	X	X	X	X	X	X	X	X	X	X	X	X	X
Concomitant Medications	X	X	X	X	X	X	X	X	X	X	X	X	X	X	X
Vital Signs (Oral Temp, Pulse, BP)	X	X			X	X			X	X	X	X	X	X	X
Physical Examination including Height and Weight	X														
Targeted PE, if indicated		X			X	X			X	X	X	X	X	X	X
Serum or Urine Pregnancy Test	X	X				X				X					
Nasal Swab Collection for SARS-CoV-2 PCR	X					X									
Blood Collection for Safety Labs	X 				X 	X 			X 	X 				X 	X 
Blood Collection for HBsAg, Anti-HCV, SARS-CoV-2 serology, HIV	X					X 									
Blood Collection for ELISpot		X				X					X	X	X	X	X
Blood Collection for ICS Assays		X				X					X			X	X
Blood Collection for Antibody Assays		X				X					X	X	X	X	X
Blood Collection for PBMC and Plasma Storage		X			X	X			X		X	X	X	X	X

Study Visit	V00	V01	V02	V03	V04	V05	V06	V07	V08	V08A	V09	V10	V11	Unsc	Early Term
Study Day post 1 st Study Vaccination	Scr-30d to -1d	D1	D2+1d	D4+2d	D8 +2d	D29±3d	D30+1d	D32+2d	D36+2d	D43+4wk	D57±3d	D209±14d	D394±14d		
Study Day post 2 nd Study Vaccination						D1	D2+1d	D4+2d	D8+2d	D15+4wk	D29±3d	D181±14d	D366±14d		
Enroll in Advantage eClinical		X													
Study Vaccination		X				X									
45 Minute Evaluation After Study Vaccination		X				X									
Distribute Memory Aid and Study Related Materials		X				X									
Review Memory Aid			X	X	X		X	X	X					X 	X 
Adverse Events		X	X	X	X	X	X	X	X		X			X 	X 
SAEs/AESIs including PIMMCs/MAAEs/NOCMCs		X	X	X	X	X	X	X	X	X 	X	X	X	X	X
Optional Leukapheresis 										X					
Saliva Collection for Antibodies			X			X				X					
Phone Call 			X	X				X	X						

 Includes WBC, HgB, PLT, ALT, AST, ALP, T Bili, CK, Cr and PT/PTT Includes WBC, HgB, PLT, ALT, AST, ALP, T Bili, CK, and Cr Safety lab per local Leukapheresis procedure If clinically indicated If within 7 days after study vaccination Includes SARS-CoV-2 serology (N-specific) only If prior to Study Visit 09 SAEs only Extra screening visit may be needed prior to Leukapheresis procedure Can be phone, text, or email contact

